### **1.6 Primary Objective**

The primary objective is to measure the change in pain from a femoral or sciatic nerve block with the use of J-tip injected lidocaine compared to needle injected lidocaine for local anesthesia prior to the regional nerve block.

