### **1.7 Secondary Objectives**

- To evaluate the difference in pain from local anesthetic infiltration with J-tip needless injection compared to needle injection.
- To evaluate efficacy of femoral and/or sciatic nerve block after J-tip lidocaine injection compared to needle injected lidocaine post operatively by tracking pain levels to post operative day three.
- To assess patient and parent satisfaction with J-tip use.
- To assess changes in post operative pain medication amounts with J-tip use.
- To evaluate changes in post operative nausea and/or vomiting with J-tip use.
- To evaluate changes in post operative anti-nausea/anti-emetic medication use with J-tip use.
- To evaluate changes in time of PACU stay.

- To assess any differences in outcomes or pain after J-tip or needle injected lidocaine with respect to BMI, thigh circumference, gender, ethnicity or operative time in pain reporting measures, satisfaction or medication usage.

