### **3. Objectives:**

#### **3.1 Primary Objective**

The primary objective is to measure the change in pain from femoral and/or sciatic nerve block with the use of the J-tip injector by visual analogue scales (VAS) for pain reporting.

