#### **3.2 Secondary Objectives**

- To evaluate the difference in pain from local anesthetic infiltration with J-tip needleless injection compared to needle injection by use of VAS.
- To evaluate efficacy of femoral nerve block after J-tip lidocaine injection post operatively by use of VAS.
- To assess patient and parent satisfaction with J-tip use by satisfaction questionnaire.
- To assess changes in post operative pain medication amounts with J-tip use.
  - 1) Type and amount in PACU
  - 2) Home log of amount taken daily for post operative days one through three (Standard opiate based pain medication prescription given to each patient). Measured in number of pills/tablets taken each day.
- To evaluate changes in post operative nausea and/or vomiting with J-tip use.
  - Calculated as “Present” or “Absent”
- To evaluate changes in post operative anti-nausea/anti-emetic medication use with J-tip use.
  - 1) Type and amount in PACU

- 2) Home record log of amount taken daily (Standard medication prescription given to each patient). Measured in number of pills/tablets taken each day.
- To evaluate time in PACU with use of J-tip compared to needle use group prior to regional block. PACU stay time recorded in minutes.

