The current observations of clinical efficacy in the delivery of local anesthesia by either needle or J-tip introduction have shown that the superficial and subcutaneous tissues are adequately anesthetized. Pain is usually encountered as the touhy needle, nerve block needle, penetrates the fascia of the muscle. The fascia is a barrier to the deeper tissues and is not anesthetized with any local anesthetic. Additional medications may be administered during the needle insertion through the fascia during the regional block. If pain VAS is greater than four, and IV Versed was not administered due to anxiety scores between four and seven, then two mg to a maximum of four mg of IV Versed will be administered. If pain continues to be above four and IV Precedex was not administered due to anxiety levels greater than seven, then 20 mcg to a max of 40 mcg IV Precedex will be administered. If pain continues to be greater than four, then 25 mcg Fentanyl to a maximum of 50 mcg will be administered. If pain values continue to be above seven, then 100 mg of IV propofol will be given. No matter what amount and type of sedative or anxiolytic is administered during the nerve block procedure, the first VAS measure at each time point will be the one of record for analysis in this study.

Patients will indicate their level of nervousness by completing a visual analogue scale, after admission to the preoperative area, for how nervous they are prior to their procedure. The anesthesiologist through observational measurement on a scale of 0-10 will also measure patient anxiety levels. A level of ten will be the highest observed measure of anxiety. These scores will assist in identifying patients that may need more general types of anesthesia prior to the nerve block. This will also allow for further evaluation of limitations due to the amount of pre-op anesthesia of patients in the study.

Femoral nerve blocks will be performed on all arthroscopic procedures. Single injection sciatic nerve blocks will be utilized in addition to femoral catheter nerve blocks for patients undergoing arthroscopic surgery with ACL reconstruction or if lateral meniscus repair is expected to be performed. The site or sites of injection on the operative lower extremity will be chosen, a timeout taken and sterile preparation performed by the

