Times will be recorded for; time of J-tip administration, time of regional block performance, operating room arrival time, incision time, surgical end time, PACU arrival time and PACU discharge time. The amount of time from regional block to arrival in operating room and to incision time will be calculated. The surgical procedure time and amount of time in PACU will also be calculated.

Visual analogue pain scales will be completed prior to and immediately after J-tip use or needle local anesthesia infiltration. The scale immediately after will be with regard to pain felt at time of J-tip use or needle introduction. The scale will be completed once again prior to and immediately after needle introduction for each regional blockade. The scale immediately after will be with regard to pain felt at time of regional block needle introduction. Visual analogue pain scale will be recorded in PACU. All scoring will be performed on separate VAS assessments without patient access to previous scores.

The patient will record visual analogue pain scales on post-operative days one through three. The anesthesiologist will collect telephone verbal pain scores on a 0-10 scale on post-operative days one and two. This is current standard procedure for all patients who

receive a regional block. The femoral nerve block catheter, when utilized, is left in place for 40 hours from the initial femoral nerve block procedure. The number of days until the post-operative visit will be recorded. Another visual analogue pain scale will be completed at the first post-operative visit. An Arthroscopic Surgery Satisfaction Questionnaire will be completed by the patient and a parent or guardian at the first post-operative visit. The questionnaire will be specific to the patient's randomized treatment group. If the patient was randomized to receive the J-Tip, the patient and parent will receive the J-Tip questionnaire and if the patient was randomized to receive the traditional needle and syringe, the patient and parent will receive the needled syringe questionnaire. The sex of the parent or guardian completing the form will be recorded.

It will also be recorded if intra-articular analgesic injection is given intra-operatively. The amount and type of pain and anti-nausea/emeitic and pain medication use will be recorded in PACU and by the patient on the first three post-operative days.

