No statistical significance when comparing means Injection Type the following variables: 1st Type of Sedation, 1st Total Quantity of sedation used (mg), 2nd Type of Sedation Used, Total Quantity 2nd Type of sedation used (mcg), 3rd Type of Sedation Used, Total Quantity 3rd Type of sedation used (mcg), Visual Analog Scale (VAS) prior to local femoral, VAS prior to femoral, VAS immediately after femoral, VAS prior to local sciatic, VAS prior to sciatic, VAS immediately after sciatic, VAS prior to PACU Discharge.

VAS Immediately After Local Femoral:

Ordinary Least Squares Regression is utilized to determine if the Visual Analog Scale (VAS) immediately after local femoral for Needle Injections is significantly different from J-Tip Injections. This regression is run to determine if the injection type can statistically predict VAS immediately after local femoral. There is an independence of residuals, as assessed by a Durbin-Watson statistic, of 1.688 (Table 4). The assumptions of linearity, independence of errors, homoscedasticity, unusual points, and normality of residuals were met. The model is statistically significant,  $F (6, 100) = 10.215, p \leq .001$ , adj.  $R^2 = .343$ . Injection type statistically significantly predicts VAS immediately after local femoral, as seen in Table 3,  $\beta = -2.020, t = -6.266, p \leq .001$ . The beta explains that if a J-tip injection was given it would decrease the VAS immediately after local femoral by approximately 2. Regression coefficients and standard errors can be found in Appendix.

Variable	Adjusted R 	Model			Injection Type		
		df	F	Sig.	Beta	T	Sig.
VAS Immediately After Local Femoral	.343	6	10.215	.000	-2.020	-6.266	.000

Table 3: Beta Explanation for VAS Immediately After Local Femoral

Model	R	R 	Adjusted R 	Standard Error of the Estimate	Durbin-Watson
1	.616 a	.380	.343	1.656	1.688

- Predictors: (Constant), Thigh Circumference (cm), Ethnicity, Injection Type, Age, Gender BMI
- Dependent Variable: VAS Immediately After Local Femoral

Table 4: Model Summary

Model		Sum of Squares	df	Mean Square	F	Sig.
1	Regression	168.140	6	28.023	10.215	.000 b
	Residual	274.327	100	2.743		
	Total	442.467	106			

a. Dependent Variable: VAS Immediately After Local Femoral  
b. Predictors: (Constant), Thigh Circumference (cm), Ethnicity, Injection Type, Age, Gender BMI

Table 5: ANOVAa

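### Pain from the regional block needle, the primary objective, is reported only as non-significant, with no N, estimate, p-value or confidence interval; every printed table shows a secondary outcome

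*Combined protocol and SAP*

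**What the plan says.** **Primary objective.** The synopsis (Section 1.6) reads: "The primary objective is to measure the change in pain from a femoral or sciatic nerve block". Section 3.1 repeats it, with VAS as the instrument: "The primary objective is to measure the change in pain from femoral and/or sciatic nerve block with the use of the J-tip injector". 

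**How it is measured.** Section 4 asks for a VAS before and immediately after each block needle. Of the second it says: "The scale immediately after will be with regard to pain felt at time of regional block needle introduction". Where sedation is given during the procedure, "the first VAS measure at each time point will be the one of record for analysis in this study".

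**Secondary objective.** Pain from the lidocaine infiltration itself is listed separately, in Section 1.7 ("To evaluate the difference in pain from local anesthetic infiltration with J-tip needless injection compared to needle injection") and in Section 3.2 ("To evaluate the difference in pain from local anesthetic infiltration with J-tip needleless injection compared to needle injection by use of VAS"). It has its own before and after VAS in Section 4.

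**Planned analysis.** Section 7 commits to exact and non-parametric tests and to 95% confidence intervals for differences. It names no primary variable, no specific test, and no rule for combining sites or handling multiplicity.

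**What is reported.** The block-needle scores appear once, in the paragraph that opens the regression part of the Results. It begins "No statistical significance when comparing means Injection Type the following variables" and closes with "VAS immediately after femoral, VAS prior to local sciatic, VAS prior to sciatic, VAS immediately after sciatic, VAS prior to PACU Discharge".

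**The concern.** The trial asks whether the way lidocaine is delivered changes the pain of the block that follows. On that question the Results offer one phrase and no figures. A statement of non-significance is compatible with two arms that are practically the same and with an interval wide enough to contain a worthwhile difference in either direction. Only an estimate with its interval separates the two, and Section 7 said intervals would be given.

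The only effect sizes a reader can take away, about 2 VAS points in favour of J-Tip at each site, belong to the infiltration. The headings over those results describe them with the words nerve blocks, so the 2-point figure is easily mistaken for the answer to the primary question. Section 4 itself explains why one cannot stand in for the other: block pain usually arises when the needle passes the fascia, which the local anesthetic does not reach.

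**Working it through.** **1. Match each score to its objective and to its results.**

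| Event | Objective | VAS planned in Section 4 | Where reported |
|---|---|---|---|
| Local infiltration | Secondary (1.7, 3.2) | Before and immediately after | After-scores: Tables 1 to 5 and 7 (femoral), Tables 1, 2 and 8 to 11 (sciatic). Before-scores: list only |
| Block needle | Primary (1.6, 3.1) | Before and immediately after each block | One list, no numbers |

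The list names the score before the local femoral injection and the score before the femoral block as separate items. The tabulated local scores are therefore not the block scores under another label.

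**2. Count the list.** It has 13 entries: six on sedation type and quantity, six VAS scores around the injections, and VAS before PACU discharge. The block needle accounts for four (before and after, femoral and sciatic). A before-to-after change is not among the 13, so on that reading of the objective not even a verdict is given. The only description of the test is a comparison of means, which is not identifiably the exact or non-parametric procedure of Section 7.

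**3. Look for the numbers elsewhere.** There is no Table 6, and the text refers to an Appendix. The femoral set (Tables 3, 4, 5, 7) and the sciatic set (Tables 8 to 11) contain the same four kinds of table, so the gap looks like a skipped number. The Appendix is cited only for regression coefficients of the local scores, which are in Tables 7 and 11, and Section 15 lists no results item. Nothing suggests that block-needle figures were placed there.

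**4. Illustrate the precision.** The documents give no figure for the block scores, so there is nothing to reproduce and the following is assumed: 54 versus 57 patients (Table 1), and a common SD of 1.5 to 2.5, which is the Table 1 range of 1.524 to 2.4553, rounded.

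Half-width of the 95% interval = t(0.975, 109) × SD × √(1/54 + 1/57) = 1.982 × 0.1899 × SD = 0.3764 × SD.

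Check against Table 2, equal-variance rows:
- Femoral: pooled SD = √[(53 × 2.133² + 56 × 1.524²)/109] = 1.845, half-width 0.694 to 0.695. Printed: (2.725 − 1.336)/2 = 0.6945.
- Sciatic: pooled SD = √[(53 × 2.4553² + 56 × 2.1631²)/109] = 2.310, half-width 0.869. Printed: (3.0974 − 1.3587)/2 = 0.869.

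The formula reproduces the printed intervals. Applied to the assumed range:
- SD 1.5: 0.3764 × 1.5 = 0.565.
- SD 2.5: 0.3764 × 2.5 = 0.941.

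With p just above 0.05 the estimate is almost one half-width from zero, so the far limit is almost two: just under 1.13 and 1.88 points. With the planned 50 per arm the multiplier is 1.9845 × 0.2 = 0.3969, giving half-widths of 0.595 and 0.992.

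**The case against.** **The null result is disclosed.** This is true. The Results say the block scores did not differ significantly, and nowhere claim that J-Tip reduced block-needle pain. A reader might infer that the primary outcome was swapped or concealed; the documents do not support that. What they show is a reporting omission and a departure from Section 7.

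**The primary variable is not defined.** This also stands. The documents state a primary objective, a change in pain, and not a primary outcome variable. Change could mean the difference between arms: Section 1.7 speaks of changes in PACU time, and Section 3.2 restates that as a comparison of the two groups. It could equally mean before to after, since both scores are collected. A reader might infer that the immediately-after score is the one primary measure. The documents do not settle it, and choosing now is post hoc. The omission does not depend on the choice, because neither reading has figures.

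**The illustration is weakly anchored.** Its SDs come from a different stimulus. They are single-arm values treated as common to both arms. The N may not apply to the sciatic block, which Section 4 plans only for some procedures, although Table 1 shows 54 and 57 at both sites. It is a t-interval for means, not the rank-based interval suggested in the fix, and it concerns the immediately-after score; the SD of a before-to-after change is not given. It shows that imprecision is possible, and no more.

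**Conclusion.** The point holds as a reporting omission on the primary objective, and it needs correcting before conclusions are drawn. That conclusion rests on reading the documents and on no assumed number: no N, summary, difference, p-value or interval for either block-needle score, against ten printed tables for a secondary outcome.

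Under the stated assumptions the 95% half-width would be about 0.6 to 0.9 points, so non-significance alone does not show that there is no difference. Two stronger inferences should be avoided. A reader might conclude that a relevant difference was missed; the documents name no meaningful difference and give no block-needle data, so this cannot be said. A reader might also assume that a re-analysis must again be non-significant; the reported verdict comes from a comparison of means, and the result of an exact or non-parametric test is not in the documents.

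**What to change.** Add one table, placed before the infiltration results and labelled primary. For the femoral and the sciatic block needle separately, give:

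- N per arm. This matters most for the sciatic block, and the regressions already use 107 patients (total df 106) where Table 1 has 111.
- Mean with SD and median with IQR per arm.
- The between-arm difference with its 95% interval, and a p-value from an exact or non-parametric test. Section 7 names none; a Wilcoxon rank-sum test with a Hodges-Lehmann interval is one suitable choice.
- Both the immediately-after VAS and the before-to-after change.

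State that the documents do not define which of the two is primary, and that any choice between them, between sites, or on multiplicity is post hoc. State which score was used when the sciatic procedure was restarted at a new location. Section 4 repeats the VAS in that case, and its first-measure rule is written about sedation, so it does not clearly settle the matter.

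Base the primary conclusion on the intervals, site by site if they disagree, and label the infiltration results as secondary.

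The cost is a small re-analysis of data already collected and one table. The primary result then shown may be non-significant or imprecise.

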## **7. Statistical Analysis Plan:**

Analyses will vary by specific aim. To evaluate our hypotheses, we will use exact and non-parametric hypothesis testing procedures. Confidence intervals (95%) of differences will be computed. Regression analysis will be employed when adjustment between comparison groups is considered necessary.

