## Results:

### Descriptive Statistics: Visual Analogy Scores (VAS) After Local Femoral and Local Sciatic Nerve Blocks

As seen in Table 1, the mean VAS immediately after local femoral for is 1.54 with a standard deviation 1.524 and the mean VAS immediately after local femoral for Needle Injections is 3.57 with a standard deviation 2.133. The mean VAS immediately after local femoral for J-Tip injections is 2.03 less than the mean VAS immediately after local femoral for Needle Injections. The difference time shows a large time gap and variation between the two injection types.

As seen in Table 1, the mean VAS immediately after local sciatic for is 2.272 with a standard deviation 2.1631 and the mean VAS immediately after local sciatic for Needle Injections is 4.5 with a standard deviation 2.4553. The mean VAS immediately after local sciatic for J-Tip injections is 2.228 less than the mean VAS immediately after local sciatic for Needle Injections. The difference time shows a large time gap and variation between the two injection types.

	Injection Type	N	Mean	Standard Deviation	Standard Error Mean
VAS Immediately After Local Femoral	Needle	54	3.57	2.133	.290
	J-Tip	57	1.54	1.524	.202
VAS Immediately After Local Sciatic	Needle	54	4.500	2.4553	.3341
	J-Tip	57	2.272	2.1631	.2865

Table 1: Group Statistics

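### The block outcomes of the primary objective have no difference or 95% CI in the supplied text, and both adjusted models, which concern a secondary outcome, omit the collected pre-injection pain VAS and use 107 of 111 patients.

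*Combined protocol and SAP*

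**What the plan says.** **Objective.** Section 3.1 states: "The primary objective is to measure the change in pain from femoral and/or sciatic nerve block with the use of the J-tip injector". Section 3.2 lists pain from the local infiltration as a secondary objective.

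**Planned analysis.** Section 7 says that "we will use exact and non-parametric hypothesis testing procedures", that "Confidence intervals (95%) of differences will be computed", and that "Regression analysis will be employed when adjustment between comparison groups is considered necessary". It names no covariates.

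**Data collected.** Section 4 has a pain VAS completed before and after the local injection, and again before and after each block needle.

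**Results.** Tables 1 and 2 and both regressions concern VAS immediately after the local injection. Each model has the same six terms: "Predictors: (Constant), Thigh Circumference (cm), Ethnicity, Injection Type, Age, Gender BMI". Neither coefficient table (Tables 7 and 11) contains a VAS term. The block outcomes appear only in one sentence of comparisons without statistical significance, which includes "Visual Analog Scale (VAS) prior to local femoral, VAS prior to femoral, VAS immediately after femoral, VAS prior to local sciatic" and goes on to VAS immediately after the sciatic block. That sentence also shows that the pre-injection VAS is in the dataset, and that it did not differ significantly between arms.

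**The concern.** A statement of non-significance for the outcomes of the primary objective does not tell the reader whether the arms were similar or the comparison was too imprecise to say. The difference and its interval would, and Section 7 commits to them.

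The adjusted models serve a secondary outcome and leave out a baseline measure of pain, a natural candidate to explain pain a moment later. If it is prognostic, adjustment would narrow the intervals for the local-injection and block outcomes using data already in hand.

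The models also rest on fewer patients than the t tests. The adjusted and unadjusted estimates therefore differ in who is included as well as in covariates. The usual assurance that covariate choice does not bias a randomised comparison does not extend to patients left out after randomisation.

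**Working it through.** **1. Reproducing the reported models.** Inputs are the sums of squares in Tables 5 and 10 and the coefficients in Tables 7 and 11.
- Femoral: R² = 168.140/442.467 = .380; adjusted R² = 1 − .620 × 106/100 = .343; F = (168.140/6)/(274.327/100) = 10.215; CI = −2.020 ± 1.984 × .322 = −2.659 to −1.381. These match within rounding.
- Sciatic: R² = 183.449/678.379 = .270; adjusted R² = .227; F = 6.178; CI −3.107 to −1.389. These match the text and Tables 9 to 11; Table 8 prints adjusted R² as .277.

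**2. Block outcomes.** No SD, SE or difference is given, so nothing can be reproduced. As a guide to scale, assume 54 and 57 patients and an SD of 1.5 to 2.5. The 95% half-width is 1.982 × SD × √(1/54 + 1/57) = 0.56 to 0.94 VAS points. The precision gain from adjustment cannot be computed for these outcomes.

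**3. Adding the pre-injection VAS to the local-injection models.** Let ρ be its partial correlation with the outcome, which the documents do not give. Ignoring chance imbalance in this VAS, the new SE = old SE × √[(1 − ρ²) × 100/99].

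| Assumed ρ | Factor | Femoral SE (now .322) | Sciatic SE (now .433) | Femoral half-width (now 0.64) |
|---|---|---|---|---|
| 0.1 | 1.000 | .322 | .433 | 0.64 |
| 0.2 | .985 | .317 | .426 | 0.63 |
| 0.3 | .959 | .309 | .415 | 0.61 |
| 0.5 | .870 | .280 | .377 | 0.56 |

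**4. The four patients.** Total df is 106 in both models, so n = 107. Table 1 has 54 + 57 = 111. Assume that the 107 are a subset of the 111.

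*Bound from total SS.* Rebuilding total SS for all 111 from Table 1 (for the needle arm, "the mean VAS immediately after local femoral for Needle Injections is 3.57 with a standard deviation 2.133"):
- Femoral: 53 × 2.133² + 56 × 1.524² + (54 × 57/111) × 2.03² = 485.5, against 442.467 in Table 5.
- Sciatic: 581.5 + 137.6 = 719.2 (unrounded sum), against 678.379 in Table 10.

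Searching all arm splits of four removed patients, with scores between 0 and 10 and the 107-patient SS fixed at the printed value, the unadjusted 107-patient difference lies in 1.86 to 2.35 (femoral) and 2.07 to 2.56 (sciatic).

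*Bound from the fitted models.* Let S = n₁n₂/107, and let R²_T be the share of variance in injection type explained by the covariates. Then residual mean square/SE² = S(1 − R²_T).
- Femoral: SE = 2.020/6.266, giving 26.397.
- Sciatic: SE = 2.248/5.191, giving 26.391.
- With S between 26.64 (50/57) and 26.75 (53/54), R²_T is about .009 to .013.

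Write the unadjusted difference as B + δ, with B taken as needle minus J-Tip. The Cauchy–Schwarz inequality gives δ²S ≤ R²_T × (SSR − B²S − 2BSδ), where SSR is the regression SS. At 53/54, the widest case:
- Femoral: SSR − B²S = 168.140 − 109.14 = 59.00, so δ runs from −0.20 to +0.15 and the difference from 1.82 to 2.17.
- Sciatic: 183.449 − 135.17 = 48.28, so δ runs from −0.19 to +0.13 and the difference from 2.06 to 2.38.

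*Both together.* Femoral 1.86 to 2.17, against 2.03 in all 111. Sciatic 2.07 to 2.38, against 2.23. The largest shift is 2.03 − 1.86 = 0.17. The reported adjusted and unadjusted estimates differ by 2.030 − 2.020 = 0.01 and 2.248 − 2.228 = 0.02.

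**The case against.** The strongest reply is that the covariate is optional. Section 7 names none and adjusts only where judged necessary, the pre-injection VAS did not differ significantly between arms, and no figure in the documents shows that it predicts injection pain. That stands: nothing prespecified was breached and the gain is unknown. But lack of a significant imbalance is not a reason to leave out a covariate that may be prognostic, and the measure is already in hand.

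Second, the supplied text may be incomplete. It refers to an appendix, and the numbering goes from Table 5 to Table 7. Block estimates or reasons for exclusion may exist elsewhere, so the claim is limited to the supplied text.

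Three stronger readings are tempting and are not supported:
- *The reported treatment effects are biased by the missing covariate.* Omitting a baseline covariate does not bias a randomised comparison.
- *Four outlying patients were deleted.* The missing SS (43.0 and 40.8) exceeds what four average patients would carry (about 17 and 26). However, the text says of the femoral model that "The assumptions of linearity, independence of errors, homoscedasticity, unusual points, and normality of residuals were met", and says the same of the sciatic model. This most naturally means that no problem was found. The same n in two models with the same covariates fits missing covariate values. If four patients were picked at random, a rough normal-approximation check gives p of about .04 and .17, which is no proof of selection.
- *The four patients could overturn the local-injection result.* The bounds above exclude this.

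**Conclusion.** The point holds, and its weight lies in the block outcomes. For the outcomes of the primary objective, the supplied text gives no difference and no interval of any kind, which leaves the commitment in Section 7 unmet there.

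The missing baseline VAS is a matter of precision only: an SE lower by about 1.5%, 4% or 13% at assumed partial correlations of 0.2, 0.3 or 0.5, and nothing at 0.10 or below. The local-injection conclusion does not change. The four unexplained omissions can move the unadjusted local-injection difference by at most about 0.17 points, provided the 107 are a subset of the 111 and the printed tables are correct. They still need a reason.

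This is a change that should be made; it is not a flaw that invalidates the reported findings. A minor note is that ethnicity takes one degree of freedom with an implied SD of at least 1.656/(√106 × .117), about 1.375 before rounding of the inputs. A 0/1 variable in 107 patients cannot exceed 0.502, so several codes appear to be fitted as one number. With coefficients of −.021 (p = .860) and .005 (p = .973), recoding would barely move the treatment term.

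**What to change.** 1. For VAS immediately after the femoral and sciatic blocks, report the treatment difference with its 95% CI twice: unadjusted (or by the planned non-parametric method), and adjusted for the pain VAS taken before the first local injection. Do not adjust for the VAS taken just before the block, because it follows the randomised treatment. State the order of the two sites: a VAS before the second local injection also follows treatment at the first.
2. Add the same baseline VAS to the two local-injection models, keep the unadjusted results alongside, and label the re-run post hoc.
3. State whether this VAS was taken before the patient knew the arm and before any sedation. Section 8 places randomisation after consent, and Section 5 allows patients to switch group once randomised, so the arm may have been known by then.
4. State why four patients were left out and from which arm. Report the adjusted analysis on all 111, with a missing-covariate method if covariates are missing.
5. As a minor item, give the ethnicity codes and enter them as indicator variables.

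The cost is a few lines of text and a re-run on existing data. The VAS uses one degree of freedom, a slight net loss if its partial correlation is below 0.10, and ethnicity indicators use a few more. If the VAS was completed after the arm was known, adjustment could absorb part of the effect, which is why the unadjusted result must stay beside it.
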